	Table 3-7.	Analysis Windows for Post-Treatment Assessments	
	Table 7-1.	Normal, Osteopenia, and Osteoporosis as Defined by T-Score	

LIST OF ABBREVIATIONS

AASLD American Association for the Study of Liver Diseases

AE adverse event

ALT alanine aminotransferase
ANCOVA analysis of covariance
ANOVA analysis of variance
Anti-HBe antibody to HBeAg
Anti-HBs antibody to HBsAg

AST aspartate aminotransferase BLQ below the limit of quantitation

BMD bone mineral density
BMI body mass index

bsAP Bone specific alkaline phosphatase

CDER Center for Drug Evaluation and Research

CFR Code of Federal Regulations

CHB chronic hepatitis B
CI confidence interval
CK creatine kinase

CKD chronic kidney disease

CKD-EPI Chronic Kidney Disease Epidemiology Collaboration formula for calculating glomerular

filtration rate

CL_{CR} creatinine clearance

CMH Cochran-Mantel-Haenszel

CRF case report form

CTX c-type collagen sequence
CV coefficient of variation
CSR clinical study report

CTCAE Common Toxicity Criteria for Adverse Events

DILI drug-induced liver injury
DMC data monitoring committee
DNA deoxyribonucleic acid

DXA dual-energy x-ray absorptiometry

ECG electrocardiogram

eCRF electronic case report form ED early discontinuation

eGFR estimated glomerular filtration rate ESDD early study drug discontinuation

FAS Full Analysis Set

FDA Food and Drug Administration

FEPO₄ fractional excretion of filtered phosphate

GFR glomerular filtration rate Gilead Gilead Sciences, Inc.

Hb hemoglobin

HBeAb hepatitis B e antibody HBeAg hepatitis B e antigen

HBsAb hepatitis B surface antibody HBsAg hepatitis B surface antigen

HBV hepatitis B virus

HCC hepatocellular carcinoma

HCV hepatitis C virus

HDL high density lipoproptein

HDV hepatitis D virus

HIV human immunodeficiency virus

HLGT high-level group term
HLT high-level term

ICH International Conference on Harmonization (of Technical Requirements for Registration of

Pharmaceuticals for Human Use)

ITT intent to treat

IWRS interactive web response system

LDL low density lipoprotein

LLN lower limit of the normal range

MDRD Modification of Diet in Renal Disease

MedDRA Medical Dictionary for Regulatory Activities

MH Mantel-Haenszel
OC osteocalcin

P1NP procollagen type 1 N-terminal propeptide

PBMC peripheral blood mononuclear cell

PCR polymerase chain reaction

PP per protocol PT preferred term

PVE Pharmacovigilance and Epidemiology

Q1, Q3 first quartile, third quartile

QD once daily

RBP retinol binding protein
SAE serious adverse event
SAP statistical analysis plan
SD standard deviation

SI ((units) international	system of units
------	--------	-----------------	-----------------

SOC system organ class
TAF tenofovir alafenamide

TDF tenofovir disoproxil fumarate (Viread®)

TFLs tables, figures, and listings

TmP tubular maximum reabsorption rate of phosphate

UACR urine albumin to creatinine ratio

ULN upper limit of normal

UPCR urine protein to creatinine ratio
WHO World Health Organization

1. INTRODUCTION

This statistical analysis plan (SAP) describes the statistical analysis methods and data presentations to be used in the tables, figures, and listings (TFLs) in the final clinical study report (CSR) for Study GS-US-320-4018. The final efficacy and safety analysis will be performed after all subjects have completed the study or prematurely discontinued the study. This SAP is based on the study protocol Amendment 1 dated 21 December 2016 and the electronic case report form (eCRF). The SAP will be finalized before database finalization for the final analysis. Any changes made after the finalization of the SAP will be documented in the CSR.

1.1. Study Objectives

The primary objectives of this study are as follows:

- To evaluate the efficacy of switching to tenofovir alafenamide (TAF) 25 mg once daily (QD) versus continuing tenofovir disoproxil fumarate (TDF) 300 mg QD in virologically suppressed subjects with chronic hepatitis B virus (HBV) as determined by the proportion of subjects with HBV DNA ≥ 20 IU/mL (as defined by the modified United States (US) Food and Drug Administration (FDA) defined snapshot algorithm) at Week 48
- To compare the safety and tolerability of switching to TAF 25 mg QD versus continuing TDF 300 mg QD in virologically suppressed subjects with chronic HBV at Week 48

The key secondary objectives of this study are as follows:

- To compare the safety of switching to TAF 25 mg QD versus continuing TDF 300 mg QD as determined by the percent change from baseline in hip and spine bone mineral density (BMD) at Week 48
- To compare the safety of switching to TAF 25 mg QD versus continuing TDF 300 mg QD as determined by the change from baseline in estimated creatinine clearance by Cockcroft-Gault method (eGFR_{CG}) at Week 48

Other secondary objectives of this study are as follows:

- To evaluate the proportion of subjects with HBV DNA < 20 IU/mL and target detected/not detected (ie, < lower limit of detection [LLOD]) at Week 48 in subjects who switched to TAF 25 mg QD versus those who continued TDF 300 mg QD
- To compare the safety of switching to TAF 25 mg QD for 96 weeks versus continuing TDF 300 mg QD for 48 weeks followed by open-label TAF for 48 weeks as determined by the percent change from baseline in hip and spine BMD at Week 96

- To compare the safety of switching to TAF 25 mg QD for 96 weeks versus continuing TDF 300 mg QD for 48 weeks followed by open-label TAF for 48 weeks as determined by the change from baseline in eGFR_{CG} at Week 96
- To compare the serological response (loss of hepatitis B surface antigen [HBsAg] and seroconversion to antibody against hepatitis B surface antigen [anti-HBs], and loss of hepatitis B e antigen [HBeAg] and seroconversion to antibody against hepatitis B e antigen [anti-HBe] in HBeAg-positive subjects) of switching to TAF 25 mg QD versus continued TDF 300 mg QD at Week 48
- To compare biochemical response (normal alanine aminotransferase [ALT] and normalized ALT) of switching to TAF 25 mg QD versus continued TDF 300 mg QD at Week 48
- To compare the change in fibrosis as assessed by FibroTest® after switching to TAF 25 mg QD versus continued TDF 300 mg QD at Week 48
- To evaluate the comparative open-label efficacy (virologic, serological, and biochemical) and safety of switching to TAF 25 mg QD from Week 48 through Week 96 in subjects initially randomized to TAF 25 mg QD and in subjects sequentially treated with continued TDF 300 mg QD for 48 weeks and then switched to open-label TAF 25 mg QD at Week 96

1.2. Study Design

1.2.1. Design Configuration and Subject Population

This is a randomized, double-blind, multicenter, active-controlled study to evaluate the safety and efficacy of TAF 25 mg QD in virologically suppressed chronic hepatitis B (CHB) subjects who switch from TDF to TAF compared to continued TDF treatment.

Approximately 460 adult (about half ≥ 50 years old) subjects with CHB, who are currently virologically suppressed while receiving therapy with TDF, will be randomized in a 1:1 ratio to receive either TAF 25 mg QD and matched placebo of TDF 300 mg QD or Gilead-provided TDF 300 mg QD and matched placebo of TAF 25 mg QD.

1.2.2. Treatment Groups and Randomization

At randomization, subjects will be stratified by screening HBeAg status (HBeAg-negative vs. HBeAg-positive) and age (≥ 50 or < 50 years).

1.2.3. Key Eligibility Criteria

Subjects were to have met all eligibility criteria, including the following key eligibility criteria:

• Documented evidence of chronic HBV infection previously (eg, documented HBsAg positive for more than 6 months)

- Maintained on TDF 300 mg QD for at least 48 weeks, and as monotherapy for CHB for at least 24 weeks prior to screening and with viral suppression (HBV DNA < lower limit of quantitation [LOQ] by local laboratory assessment) for a minimum of 12 weeks prior to screening, and including a screening HBV DNA value of < 20 IU/mL (by a central laboratory)
- Estimated creatinine clearance ≥ 50 ml/min (using the Cockcroft-Gault method) based on serum creatinine and actual body weight as measured at screening
- Did not have co-infection with hepatitis C virus (HCV), HIV, or hepatitis D virus (HDV), evidence of hepatocellular carcinoma or recent (≤ 5 years) history of clinical hepatic decompensation, and abnormal hematological and biochemical parameters

1.2.4. Study Periods and Phases

The duration of double-blind treatment is 48 weeks. All subjects who complete 48 weeks of treatment are eligible for participation in the open label TAF 25-mg extension period for an additional 48 weeks (through Week 96). During the double-blind period only, subjects with a confirmed eGFR $_{CG}$ < 50 ml/min, and > 20% decline in estimated glomerular filtration rate (eGFR $_{CysC}$) by CKD-EPI (cystatin C) compared to baseline during the study, were required to undergo dose modification to every other day dosing of study drug. Subjects with confirmed creatinine clearance < 30 mL/min during the double-blind period of the study were to have the study drug discontinued.

1.2.5. Schedule of Assessments

Laboratory analyses (serum chemistry and liver tests, hematology, eGFR_{CG}, urinalysis, plasma HBV DNA levels), pregnancy testing [for females of childbearing potential]), vital signs, adverse events, and concomitant medications will be measured or assessed at screening baseline, Weeks 4, 8, 12, 24, 36, 48, 60, 72, and 96 (and at early discontinuation [ED]). Fasting metabolic panels will be measured at baseline, and Weeks 12, 24, 36, 48, 60, 72, and at 96 (and at ED). HBV serology (HBsAg, HBeAg, reflex hepatitis B antibody [HBeAb], hepatitis B surface antibody [HBsAb], and quantitative HBsAg) will be conducted at screening, baseline, Weeks 12, 24, 36, 48, 60 72, and 96 (and at ED).

Dual energy x-ray absorptiometry (DXA) scans of the hip and spine will be performed at baseline and Weeks 24, 48, 72, and 96 (and at ED). Bone and renal biomarker testing will be performed at baseline and Weeks 4, 12, 24, 48, 72, and 96 (and at ED). FibroTest® and the Child Pugh Score will be performed at baseline, Week 48, and Week 96 (and at ED).

Complete physical examination will be performed at screening, baseline, and Weeks 24, 48, 72, and 96 (and at ED). Symptom-driven physical examinations including body weight assessment will be conducted at all other visits. Electrocardiogram (ECG) will be performed at screening, Week 48, and Week 96 (and at ED). Health-related quality of life questionnaires including Chronic Liver Disease Questionnaire (CLDQ), SF-36, and Work Productivity and Activity Impairment (WPAI) will be filled out at baseline, and Weeks 24, 48, and 96 (and at ED).

Follow-up assessments will occur every 4 weeks for 12 weeks for subjects who discontinue study drug due to HBsAg loss and for 24 weeks for subjects who permanently discontinue study drug for other reasons, and will include the following: concomitant medications, adverse events, body weight, vital signs, symptom driven physical examinations, laboratory analyses, and HBV serology.

1.3. Sample Size and Power

With respect to the primary efficacy endpoint of proportion of subjects with HBV DNA \geq 20 IU/mL (the lower LOQ of the current polymerase chain reaction [PCR] assay), as determined by the modified US FDA-defined snapshot algorithm, at Week 48, when the sample sizes are 230 (TAF 25 mg arm) and 230 (TDF 300 mg arm), a two-group, large-sample normal approximation test of proportions with a one-sided 0.025 significance level will have 80% power to establish non-inferiority of TAF to TDF. It is assumed that both treatment arms will have subjects who have HBV DNA \geq 20 IU/mL (as defined by the modified US FDA-defined snapshot algorithm) at a rate of 2.4% at Week 48 (based on the rates of suppressed subjects having HBV DNA \geq 29 IU/mL, the lower LOQ of the assay used in those studies, after 48 weeks of treatment from the combined data from TDF studies GS-US-174-0102 and GS-US-174-0103 with the ratio of HBeAg- to HBeAg+ subjects assumed to be 2:1), with a non-inferiority margin of 4%.

The proposed sample size (n 230 for the TAF 25 mg arm, n 230 for the TDF 300 mg arm) also provides > 99% power to detect a 1.81% difference in the percentage change from baseline in hip BMD at Week 48 (assuming a 1.47% [SD 2.71%] change from baseline in the TAF 25 mg arm and 0.34% [SD 2.83%] change from baseline in the TDF 300 mg arm, with a two-sided α 0.05); a > 99% power to detect a 2.00% difference in the percentage change from baseline in spine BMD at Week 48 (assuming a 1.56% [SD 3.84%] change from baseline in the TAF 25 mg arm and 0.44% [SD 4.14%] change in the TDF 300 mg arm, with a two-sided α 0.05); a 97% power to detect a 4.9 mL/min difference in the change from baseline in eGFR_{CG} at Week 48 (assuming a 1.3 mL/min [SD 13.2] change from baseline in the TAF 25 mg arm and 3.6 mL/min [SD 13.0] change from baseline in the TDF 300 mg arm, with a two-sided α 0.05). These assumptions were derived from an HIV switch study (GS-US-292-0109) due to the unavailability of stable and suppressed switch data from TAF HBV studies.

2. TYPE OF PLANNED ANALYSIS

2.1. Data Monitoring Committee (DMC) Analysis

An external multidisciplinary Data Monitoring Committee (DMC) will review the progress of the study and perform interim reviews of the safety data in order to protect subject welfare and preserve study integrity. To ensure the best interests of the participants, the DMC will recommend to the sponsor if the nature, frequency, and severity of adverse effects associated with the study treatment warrant the early termination of the study, the continuation of the study, or the continuation of the study with modifications.

The initial review was conducted after all subjects completed 24 weeks of the study. No additional meetings were requested by the DMC.

The DMC's role and responsibilities and the scope of analysis to be provided to the DMC are provided in a mutually agreed upon charter, which defines the DMC membership, meeting logistics, and meeting frequency.

2.2. Week 48 Analysis (Primary Analysis)

The Week 48 analysis was conducted after the last subject completed the Week 48 visit or prematurely discontinued study drug.

2.3. Final Analysis

The final analysis for the study will be conducted after all subjects have completed the study or prematurely discontinued the study, for all study data from double-blind phase to open-label phase to treatment-free follow-up.

This SAP described the plan for the final analysis.

3. GENERAL CONSIDERATIONS FOR DATA ANALYSES

Analysis results will be presented using descriptive statistics. For categorical variables, the number and percentage of subjects in each category will be presented; for continuous variables, the number of subjects (n), mean, standard deviation (SD) or standard error (SE), median, first quartile (Q1), third quartile (Q3), minimum, and maximum will be presented.

By-subject listings will be presented for all subjects in the Randomized Analysis Set and sorted by subject ID number, visit date, and time (if applicable). Data collected on log forms, such as adverse events (AEs), will be presented in chronological order within the subject. The treatment group to which subjects were randomized will be used in the listings. Age, sex at birth, race, and ethnicity will be included in the listings, as space permits.

3.1. Analysis Sets

Analysis sets define the subjects to be included in an analysis. Analysis sets and their definitions are provided in this section. The analysis set will be identified and included as a subtitle of each table, figure, and listing.

For each analysis set, the number and percentage of subjects who were included out of all randomized subjects will be summarized by treatment group and overall.

A listing of reasons for exclusion from analysis sets will be provided by subject.

3.1.1. Randomized Analysis Set

The Randomized Analysis Set includes all subjects who were randomized into the study. This is the primary analysis set for by-subject listings.

3.1.2. Safety Analysis Set

The Safety Analysis Set will include all randomized subjects who have received at least 1 dose of study drug. Subjects will be analyzed according to the treatment they actually received during the double-blind phase. The actual treatment received will differ from the randomized treatment only when their actual treatment differs from randomized treatment for the entire treatment duration during the double-blind phase. This is the primary analysis set for safety analyses.

3.1.3. Open-Label Safety Analysis Set

The Open-Label Safety Analysis Set includes all randomized subjects who have received at least 1 dose of open-label study drug. Subjects will be analyzed according to the treatment they actually received during the double-blind phase.

3.1.4. Treatment-Free Follow-up Safety Analysis Set

The treatment-free follow-up (TFFU) Safety Analysis Set includes all randomized subjects who entered the TFFU period. Subjects will be analyzed according to the treatment they actually received during the double-blind phase.

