3. STUDY DESIGN

3.1. Study Treatment Plan and Regimen

This is a randomized, double-blind, multicenter, active-controlled study to evaluate the safety and efficacy of TAF 25 mg QD in virologically suppressed subjects who switch from TDF to TAF compared to continued TDF treatment.

Approximately 460 subjects (with approximately 50% of subjects being \geq 50 years old) will be randomized in a 1:1 ratio (A:B) to receive either TAF 25 mg QD and matched placebo of TDF 300 mg QD or Gilead-provided TDF 300 mg QD and matched placebo of TAF 25 mg QD.

At randomization, subjects will be stratified by screening HBeAg status (HBeAg-negative vs. HBeAg-positive) and age (> 50 or < 50 years).

- Treatment Arm A: approximately 230 subjects administered TAF 25 mg QD and matched placebo of Tenofovir DF (TDF) 300 mg QD
- Treatment Arm B: approximately 230 subjects administered Gilead-provided TDF 300 mg QD and matched placebo of TAF 25 mg QD

The duration of double blind treatment is 48 weeks. All subjects who complete 48 weeks of treatment are eligible for participation in the open label TAF 25 mg extension period for an additional 48 weeks (through Week 96). During the double-blind period, subjects with a confirmed creatinine clearance by Cockcroft Gault Method (eGFR_{CG}) < 50 ml/min, and > 20% decline in eGFR by CKD-EPI (cystatin C) compared to baseline during the study, will be required to undergo dose modification to every other day dosing of study drug. Subjects with confirmed creatinine clearance < 30 mL/min during the double blind phase of the study will have the study drug permanently discontinued. Subjects with confirmed eGFR_{CG} < 50 mL/min will not undergo dose modification to every other day during the open-label TAF 25 mg extension period, nor will treatment be permanently discontinued for confirmed eGFR_{CG} < 30 mL/min during the open-label extension period.

Subjects who permanently discontinue study drug (either prematurely or at the end of study [Week 96]) for reasons other than HBsAg loss with confirmed seroconversion to anti-HBs will be followed every 4 weeks for 24 weeks off treatment or until initiation of appropriate alternative, HBV therapy, whichever occurs first. Use of appropriate, alternative HBV therapy is strongly encouraged.

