6.4.2. All Other Subjects Who Discontinue Study Drug

Subjects who have received at least one dose of study drug and permanently discontinue study drug for reasons other than HBsAg loss with confirmed seroconversion to anti-HBs will be followed every 4 weeks for 24 weeks off treatment or up to initiation of appropriate, alternative HBV therapy, whichever occurs first.

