7.2.2. Assessment of Severity

Severity of adverse events is to be determined based on GSI Grading Scale for Severity of Adverse Events and Laboratory Abnormalities (Appendix 4). A distinction should be drawn between seriousness and severity of AEs. An AE that is assessed as Grade 4 (potentially life-threatening) should not be confused with an SAE. Severity is a category utilized for rating the intensity of an event: both AEs and SAEs can be assessed as Grade 4. An event is defined as "serious" when it meets one of the predefined outcomes described above in Section 7.1.2.

7.3. Investigator Requirements and Instructions for Reporting Adverse Events and Serious Adverse Events to Gilead

Requirements for collection prior to study drug initiation:

After informed consent, but prior to initiation of study medication, the following types of events should be reported on the case report form (CRF/eCRF): all SAEs and adverse events related to protocol-mandated procedures.

Adverse Events

Following initiation of study medication, collect all AEs, regardless of cause or relationship, until 30-days after last administration of study IMP must be reported to the CRF/eCRF database as instructed.

All AEs should be followed up until resolution or until the adverse event is stable, if possible. Gilead Sciences may request that certain AEs be followed beyond the protocol defined follow up period.

Serious Adverse Events

All SAEs, regardless of cause or relationship, that occurs after the subject first consents to participate in the study (ie, signing the informed consent) and throughout the duration of the study, including the protocol-required post treatment follow-up period, must be reported to the CRF/eCRF database and Gilead Drug Safety and Public Health (DSPH) as instructed. This also includes any SAEs resulting from protocol-associated procedures performed after informed consent is signed.

Any SAEs and deaths that occur after the post treatment follow-up visit but within 30-days of the last dose of study IMP, regardless of causality, should also be reported.

Investigators are not obligated to actively seek SAEs after the protocol defined follow up period; however, if the investigator learns of any SAEs that occur after study participation has concluded and the event is deemed relevant to the use of IMP, he/she should promptly document and report the event to Gilead DSPH.

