7.1.6. Treatment-Emergent AEs

7.1.6.1. Definition of Treatment-Emergent

Treatment-emergent AEs will be separately defined for the double-blind phase and the open-label phase. Post-treatment-emergent AEs will be defined only for the TFFU phase.

Treatment-emergent AEs occurring during the double-blind phase are defined as:

- Any AE with onset date on or after the blinded study drug start date and no later than the minimum of the blinded study drug stop date + 3 days and the day prior to the first dose date of open-label study drug, if applicable, for those who discontinued blinded study drug permanently, or
- Any AE with onset date on or after the blinded study drug start date for those who are still on the blinded study drug, or
- Any AE leading to blinded study drug discontinuation.

Treatment-emergent AEs occurring during the open-label phase are defined as:

- Any AE with onset date on or after the open-label study drug start date and no later than the open-label study drug stop date + 3 days for those who discontinued open-label study drug permanently, or
- Any AE with onset date on or after the open-label study drug start date for those who are still on open-label study drug, or
- Any AE leading to open-label study drug discontinuation.

Post-treatment-emergent AEs occurring during the TFFU phase are defined as:

Any AE with onset date after the last dose of study drug + 3 days

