7.1.7. Summaries of AEs and Deaths

AEs will be summarized for (1) subjects in the Safety Analysis Set during the double-blind phase, (2) subjects in the Open-Label Safety Analysis Set during the open-label phase, and (3) subjects in the TFFU Safety Analysis Set during the TFFU phase. The full set of AE summaries as described below will be generated for (1) and (2).

A brief summary of AEs (ie, the number and percentage of subjects) will be presented by treatment group for the following: any treatment-emergent AE, any Grade 3 or 4 treatment-emergent AE, any Grade 2, 3 or 4 treatment-emergent AE, any treatment-emergent study drug-related AE, any Grade 2, 3 or 4 treatment-emergent study drug-related AE, any Grade 2, 3 or 4 treatment-emergent study drug-related AE, any treatment-emergent serious adverse event (SAE),

any treatment-emergent study drug-related SAE, any treatment-emergent AE leading to premature study drug discontinuation, any treatment-emergent AE leading to dose modification or study drug interruption, and any death.

Summaries (number and percentage of subjects) of AEs (by SOC, HLT [if specified below], and PT) will be provided by treatment group and overall as follows:

- All treatment-emergent AEs summarized by SOC, HLT, and PT
- Any Grade 3 or 4 treatment-emergent AEs
- Any Grade 2, 3, or 4 treatment-emergent AEs
- All treatment-emergent nonserious AEs occurring in at least 5% of subjects in any treatment group (this summary is generated per requirement for reporting in ClinicalTrials.gov)
- All treatment-emergent study drug-related AEs summarized by SOC, HLT, and PT
- Any Grade 3 or 4 treatment-emergent study drug-related AEs
- Any Grade 2, 3, or 4 treatment-emergent study drug-related AEs
- All treatment-emergent SAEs
- All treatment-emergent study drug-related SAEs
- All treatment-emergent AEs leading to premature discontinuation from study drug
- All treatment-emergent AEs leading to dose modification or study drug interruption

Multiple events will be counted once only per subject in each summary. For data presentation, SOC (and HLT) will be ordered alphabetically, with PT sorted by decreasing total frequency. For summaries by severity grade, the most severe event will be selected.

For post-treatment AEs during the TFFU phase, the overall summary and individual summaries will be provided only for the following:

- All post-treatment-emergent AEs
- Any Grade 3 and 4 post-treatment-emergent AEs
- All post-treatment-emergent SAEs

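### AEs and SAEs that start 4 to 30 days after the last dose are collected from every treated subject, but the SAP tabulates them only for subjects who entered treatment-free follow-up

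*SAP*

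**What the plan says.** **Collection.** Under Protocol 7.3, once study medication has started, sites must "collect all AEs, regardless of cause or relationship, until 30-days after last administration of study IMP". The same section also asks for "Any SAEs and deaths that occur after the post treatment follow-up visit but within 30-days of the last dose of study IMP". Neither rule depends on entering treatment-free follow-up (TFFU).

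**Treatment-emergent window.** SAP 7.1.6.1 closes the open-label window "no later than the open-label study drug stop date + 3 days for those who discontinued open-label study drug permanently". The double-blind window closes at the blinded stop date + 3 days, or on the day before the first open-label dose if that is earlier. An AE that led to drug discontinuation counts whatever its onset date. AEs that start later are called post-treatment-emergent, a term the SAP defines for the TFFU phase only.

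**Tables.** SAP 7.1.7 begins "AEs will be summarized for (1) subjects in the Safety Analysis Set during the double-blind phase" and adds two further populations: the Open-Label Safety Analysis Set in the open-label phase and the TFFU Safety Analysis Set in the TFFU phase. It names no other. SAP 3.1.4 defines the last of these: "The treatment-free follow-up (TFFU) Safety Analysis Set includes all randomized subjects who entered the TFFU period".

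**Who has a TFFU period.** Under Protocol 6.4.2, subjects who stop for reasons other than HBsAg loss with confirmed seroconversion are "followed every 4 weeks for 24 weeks off treatment or up to initiation of appropriate, alternative HBV therapy, whichever occurs first". Protocol 3.1 adds: "Use of appropriate, alternative HBV therapy is strongly encouraged". Protocol 3.3 (End of Study) makes the off-treatment weeks after Week 96 conditional on other anti-HBV treatment not being started. SAP 4.1 counts entry into TFFU as a disposition category of its own.

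**The concern.** The population for collection and the population for tabulation differ. Everyone who stops study drug is under AE collection for 30 days. Only those who entered TFFU can contribute an event after day 3 to a table. The route the protocol encourages, prompt use of other HBV therapy, leads out of the only table that covers this period.

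The post-treatment AE and SAE tables would then describe subjects who stayed off therapy, a group selected by clinical decision. A reader of the study report would find no tabulated count of events in the month after stopping for everyone who stopped, although the data are in the database.

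**Working it through.** The documents give no figure on this point to reproduce. The check has two parts: a classification that needs no assumption, and a rough size that does.

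**1. Where an event goes, by onset day after the last dose** (windows from SAP 7.1.6.1, table populations from SAP 7.1.7 and 3.1.4, collection period from Protocol 7.3)

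| Onset day | Entered TFFU | Did not enter TFFU |
|---|---|---|
| 1 to 3 | Treatment-emergent table | Treatment-emergent table |
| 4 to 30 | TFFU table | Listing only |

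Days 4 to 30 are 30 − 3 = 27 of the 30 collection days. For a subject who skips TFFU, 3 of 30 days reach an AE table.

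Three exceptions narrow the listing-only cell:
- AEs that led to drug discontinuation are treatment-emergent whatever their onset (SAP 7.1.6.1).
- AEs with partial or missing onset dates can default into a treatment-emergent table (SAP 7.1.6.2).
- The any-death row of the brief summary in SAP 7.1.7 has no stated time limit, so a late death may be counted there.

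**2. Rough size**

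Inputs from the Phase 3 TAF group (Protocol 1.2.3, Tables 1-5 and 1-6): 70.2% with any AE, 4.2% with an SAE, mean exposure 58.9 weeks. Planned number of subjects: 460. Assumptions: constant hazard, the same event rate after stopping as on treatment, and a share skipping TFFU of 25% to 95%. The documents do not give this share.

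Hazard per week = −ln(1 − p) / 58.9. Risk over 27 days (27/7 = 3.857 weeks) = 1 − exp(−hazard × 3.857).

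- AE: −ln(0.298)/58.9 = 0.0206 per week; risk = 1 − exp(−0.0793) = 7.6%.
- SAE: −ln(0.958)/58.9 = 0.00073 per week; risk = 1 − exp(−0.0028) = 0.28%.

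| Assumed share skipping TFFU | Subjects | Subject-weeks (× 27/7) | With an AE | With an SAE |
|---|---|---|---|---|
| 25% | 115 | 444 | 8.8 | 0.3 |
| 50% | 230 | 887 | 17.5 | 0.6 |
| 90% | 414 | 1,597 | 31.6 | 1.2 |
| 95% | 437 | 1,686 | 33.3 | 1.2 |

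The AE column is likely too high. The source rate came from subjects seen at regular visits, whereas a subject who skips TFFU may have no visit in the window and report only passively.

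**The case against.** The strongest reply is that nothing promised is missing. Protocol 7.3 is a rule for collection and reporting, not for tables. Protocol 8.7 commits to summarising safety data up to the last dose and to listing treatment-free follow-up data. Protocol 8.2.1.3 lets follow-up data be either summarised or listed. Protocol 8.7.3 closes the treatment-emergent period at the last dose, apart from AEs that cause discontinuation. The SAP already goes further, with 3 extra days and a TFFU table. All of this stands, so a reader who infers that the SAP breaches the protocol would be wrong.

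A reader might also infer that the events are lost. They are not. SAP section 7 puts all safety data in listings, and SAP 7.1.7 provides listings of all AEs, Grade 3 and 4 AEs, SAEs and deaths. For about one SAE subject, a listing is workable.

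The restriction also has a rationale: the TFFU table is labelled by its analysis set and describes subjects off therapy, while an event after an immediate switch occurs on non-study therapy. That justifies keeping the TFFU table. It does not justify having no count for the others.

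Finally, entry into TFFU is not defined beyond the disposition category, and SAP 1.2.5 describes the 24-week follow-up without the alternative-therapy condition. A broad reading of entry would shrink the gap. Protocol 3.1 and 3.3 do not support that reading for a subject who switches at once, but the affected share remains unknown.

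**Conclusion.** The point holds as a gap in the SAP's choice of table population. For subjects who stop study drug and do not enter TFFU, AEs and SAEs with onset on days 4 to 30 appear in listings only, apart from the three exceptions above. The 27-of-30-day figure follows from the text. The subject counts do not: they rest on an assumed share skipping TFFU and on on-treatment rates carried past the last dose. About one SAE subject or fewer is plausible.

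A reader might infer that the study's AE and SAE results are materially understated, or that the comparison of arms is biased. The documents do not support either. SAP 7.1.7 specifies no between-group AE test, and subjects from both arms who continue past Week 48 take open-label TAF. The Week 48 analysis was done under a separate SAP that is not among these documents. This is a minor reporting improvement.

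**What to change.** In SAP 7.1.7, add one descriptive table of all AEs, Grade 3 and 4 AEs, and SAEs with onset from last dose + 4 to last dose + 30 days. Base it on all Safety Analysis Set subjects who permanently stopped study drug, with separate columns or rows for those who did and did not enter TFFU according to the SAP 4.1 disposition data.

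Split by TFFU entry, not by dated use of other HBV therapy. Protocol 5.4 records concomitant medication only up to the last study visit, so a switch made after that visit may have no date on record. Keep the existing TFFU table, and footnote that day 4 to 30 events of subjects who entered TFFU appear in both.

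The cost is a short addition to the SAP text and one table from data already collected. If the SAP is already final, the change can be documented in the study report, as SAP section 1 provides. The downsides belong in a footnote: some added events will have occurred on non-study HBV therapy, and reporting after the last visit is passive. No visit, dose or clinical rule changes.
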